4.0 Human Subjects

4.1 General Characteristics – Minority Inclusion and Non-Discriminatory Statements

Adult patients with SCD (HbSS, SC, or S β^0) aged 18 years or older admitted to UPMC (Presbyterian, Montefiore, Magee, Shadyside) hospitals with a diagnosis of ACS will be eligible for screening to participate in the trial. Children and pregnant females will not be enrolled in the study. Any patient with a predisposition towards thrombosis, other than SCD, and bleeding, as detailed in the inclusion and exclusion criteria, will be excluded from study participation. Specifically, moyamoya disease has a 20% incidence of intracranial hemorrhage in adults in the United States.¹⁶ The incidence of the disease is 1 in 1 million in the United States; therefore, even with an increased association between moyamoya disease and SCD, it is unlikely to affect patient recruitment.¹⁶ Additionally, proliferative retinopathy predisposes towards vitreous hemorrhages with visual loss; however, the incidence of the disease is 0.5 per 100 patients, which, again, will be unlikely to affect patient recruitment.¹⁷

As SCD is an autosomal recessive disorder that predominantly affects individuals of African descent, it is anticipated that the study population will be comprised largely of African Americans, and the percentage of male and female participants will be similar in number. There will be no discrimination based on gender, race, or ethnicity. The gender, racial, and ethnic characteristics of the proposed study population will reflect the demographics of the disease, the city of Pittsburgh and surrounding areas, and UPMC. Written informed consent will be obtained from all subjects prior to enrollment in the study.

4.2 Recruitment Procedures

Patients with SCD will be given a flyer presenting the study during SCD clinic visits to produce study awareness and increase the likelihood of future study participation. All subjects will be enrolled at UPMC (Presbyterian, Montefiore, Magee, Shadyside) hospitals. The SCD inpatient service, including Drs. [name] and [name], two of the study co-investigators, is consulted to assist in the management of all hospitalized patients with SCD. Individuals approached for participation in this study will be subjects age 18 years or older admitted to one of the aforementioned hospitals with a diagnosis of ACS. A member of the research staff will meet with prospective subjects during inpatient admission and determine the patient's interest in study participation, and if interested, discuss the study in further detail. Informed consent will be obtained by [name], and include the purpose of the study, protocol specifics as they relate to the patient, potential adverse effects, and risks and benefit of the study. Each potential subject will be encouraged to ask all questions that he or she feels are necessary to enable him or her to make an informed decision regarding participation in the study. Each potential subject will be encouraged to take the time needed for thoughtful consideration whether or not to participate in the study; however, due to the design of the trial, which requires randomization within 24 hours of the diagnosis of ACS, there will be some time constraints with respect to the decision regarding study participation. Subjects who read the consent form are free to refuse enrollment. No experimental interventions will occur until after informed consent is obtained.

Subjects will be considered enrolled in the study after informed consent is obtained. Each study participant will receive a unique subject identification number. Afterwards, screening assessment will be completed by a member of the research staff. All individuals will have any reason for study exclusion documented. Following enrollment and screening, patients will undergo randomization. Prior to beginning the study, an independent statistician will perform a 1:1 randomization using randomization software ensuring 10 patients are placed in each arm of the study. A card will be labeled heparin or standard of care, placed in a sealed envelope numbered 1 to 20, and stored in locked files at HCWP. Following enrollment and screening, a member of the research staff will access the appropriate numbered envelope to ascertain patient assignment.

Study participants will be free to withdraw at any time by notifying a member of the research staff. Any data collected prior to the time of withdrawal will continue to be used, but no additional information will be collected. Processed blood sample results will continue to be used; however, remaining samples will be destroyed or used as indicated by the subject. The reason and date of study withdrawal for all subjects will be recorded.

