Further data collected will include information regarding standard of care therapy (collected daily during duration of study), demographics (collected following study enrollment and screening), and medical information (collected following study enrollment and screening). Regarding standard of care therapy, data collected will consist of whether or not intravenous fluids were given; whether or not antibiotics were administered, number of antibiotics received, and class of antibiotics given (penicillin, cephalosporin, macrolide, fluoroquinolone, vancomycin, other); whether or not supplemental oxygen was received with documentation of need for noninvasive positive pressure ventilation or mechanical ventilation; whether or not pain medication was provided, including type of pain medication (opioid, NSAIDs, acetaminophen, other); number of red blood cell transfusions given; and whether or not exchange transfusion was necessary. Demographics include age, race, and sex. SCD related medical information includes number of previous episodes of ACS, current administration of outpatient hydroxyurea, and prior DVT or PE. General medical information includes history of myocardial infarction; chronic lung disease, defined as a documented baseline arterial oxygen saturation less than 90% and/or home supplemental oxygen requirement; previous stroke; and current or former smoker.

Prespecified feasibility criteria are as follows: the ability to enroll potential study participants, which includes the timely notification of hospitalized patients with ACS, the capacity to consent eligible individuals, and the ability to appropriately randomize screened patients within 24 hours of diagnosis, all of which should occur at a frequency greater than or equal to 80%; inclusion and exclusion criteria that does not exclude potential study participants at a frequency greater than or equal to 20%; the proper administration of the study drug at a frequency greater than or equal to 90%; and the ability to completely and accurately collect clinical data of interest at frequency greater than or equal to 90%. The final aim of our pilot study is to provide preliminary data, with respect to treatment effect and variance, for future sample size calculations given the lack of existing data to help guide this process.

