
Potential adverse events include heparin-associated risks, such as allergic reaction, major bleeding, minor bleeding, thrombocytopenia, and heparin induced thrombocytopenia (HIT), or any other adverse reaction suspected secondary to drug administration. All subjects enrolled in the study and received any UFH will be included in the safety evaluation.

A member of the research staff will collect the study data. All data required by the study protocol will be documented in the inpatient electronic medical record system. De-identified subject information will be written on Case Report Forms (CRFs) and all data collected will be stored in locked files at the Hemophilia Center of Western Pennsylvania (HCWP). Additionally, data will be entered into research electronic capture (REDCap) and compared to ensure consistency. No personal identifiers will be associated with the data. The Institutional Review Board (IRB) may inspect records at any time.

A sample size of 20 subjects for the pilot study is based on clinical rather than statistical considerations and should provide a preliminary estimate of primary and secondary clinical outcomes and assess prespecified feasibility criteria as detailed above. Based on 75,000 to 100,000 African Americans with SCD in the United States who develop ACS at a frequency of 8.8 per 100 patient years, with 50% developing ACS at some point during his or her lifetime, and given the fact that approximately 30 patients are admitted annually at UPMC hospitals (Presbyterian, Montefiore, Magee, Shadyside) with ACS, we estimate that at least 80%, or 24 patients per year, will meet inclusion and exclusion criteria, and expect to enroll 10 patients, or slightly less than 50% per year, which should meet the n=20 subjects required for the pilot study.^{3,4} This is a pilot feasibility study, so comparisons will be descriptive, including frequencies and percentages for categorical variables and mean, median, range, and standard deviation for continuous variables.

Demographics and medical information will be summarized with descriptive statistics as well. Adverse events will be summarized by frequency, relatedness, and severity.

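### Formal eligibility screening follows consent, so the plan as written does not record the denominator that its 20% exclusion limit and its 80% consent criterion need

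*Combined protocol and SAP*

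**What the plan says.** Section 4.2 (Recruitment Procedures) sets the sequence. Research staff approach adults admitted to the named hospitals with a diagnosis of ACS and seek consent. Then: "Subjects will be considered enrolled in the study after informed consent is obtained". An identification number is assigned, and "Afterwards, screening assessment will be completed by a member of the research staff". The next sentence reads "All individuals will have any reason for study exclusion documented". Randomization by numbered envelope comes last.

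Section 3.3 sets the feasibility criteria. One is "inclusion and exclusion criteria that does not exclude potential study participants at a frequency greater than or equal to 20" percent. Another is "the capacity to consent eligible individuals", to be met at a frequency of at least 80%.

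The accrual projection, also in Section 3.3, starts from "approximately 30 patients are admitted annually at UPMC hospitals" with ACS. It continues "we estimate that at least 80%, or 24 patients per year, will meet inclusion and exclusion criteria", and the sponsor then expects to "expect to enroll 10 patients, or slightly less than 50% per year".

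**The concern.** The procedure and the criteria refer to different groups of people. Followed literally, Section 4.2 applies the ten exclusion criteria of Section 4.3 only to people who have already consented. Before that, the approach is filtered on age, hospital and ACS diagnosis alone. The exclusion limit and the 24-of-30 projection concern the wider group from which consenters come.

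The consent criterion has the same gap. Its denominator is eligible patients, including those who refuse, and the sequence never establishes whether a refuser was eligible.

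Whether the eligibility criteria are workable and whether eligible patients will consent are both stated feasibility objectives, in a study whose purpose is to judge the feasibility of a larger trial. If neither rate has its proper denominator, the pilot reports on two of its own objectives with figures from a self-selected subset.

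**Working it through.** **Inputs.** From Section 3.3: about 30 ACS admissions a year, at least 80% eligible, 10 enrolled a year, 20 in total. From Section 4.2: 20 envelopes, so the 20 are taken here as randomized patients. Assumption: the 20% exclusion implied by the projection also applies among consenters.

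**The plan's own figures.** 30 × 0.80 = 24 eligible a year, as stated. 10/24 = 41.7%, which fits the description of slightly under half. 20/10 = 2 years, hence 60 admissions.

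**How many would be screened.** Consenters needed = randomized / (1 − exclusion rate).
- Per year: 10/0.80 = 12.5 of 30. Without eligibility data: 17.5/30 = 58%.
- Over two years: 20/0.80 = 25 of 60, with 5 exclusions seen and 35 admissions not formally assessed.
- If the 10 a year are instead consenters (the Section 4.2 meaning of enrolled), 20/30 = 67% have no data.

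**What the observed rate says about all admissions.** Overall rate = g × (rate in consenters) + (1 − g) × (rate in the rest), where g is the share screened. With g = 25/60 = 0.417 and 20% seen in consenters:
- if none of the other 35 would be excluded: 5/60 = 8.3%
- if all would be: (5 + 35)/60 = 66.7%

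These are logical bounds. The documents give no exclusion rate for non-consenters, so the values below are assumptions that show the range.

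| Rate in consenters | Consenters for 20 randomized | Assumed rate in the rest | Overall rate |
|---|---|---|---|
| 20% | 25 (g = 0.417) | 10% | 14.2% |
| 20% | 25 | 30% | 25.8% |
| 10% | 20/0.90 = 22.2 (g = 0.370) | 10% | 10.0% |
| 10% | 22.2 | 30% | 22.6% |
| 10% | 22.2 | 40% | 28.9% |

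With 10% seen in consenters (an apparent pass), the overall rate reaches 20% once the rest are excluded at (0.20 − 0.370 × 0.10)/0.630 = 25.9%. The first row shows an error in the other direction: 20% in consenters fails the limit, while the overall 14.2% would meet it.

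**Precision (Clopper-Pearson 95%).** 5/25 = 20%: 6.8% to 40.7%. With all 60 logged at the same rate, 12/60 = 20%: 10.8% to 32.3%.

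**Consent criterion.** If eligibility is established only after consent, everyone known to be eligible has consented, and the ratio is 100% by construction. On the plan's own projection, enrolled over all eligible is 10/24 = 41.7%. That figure mixes refusals with patients missed or not approached, which is why approach status has to be recorded too.

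**The case against.** The strongest reply is that other text implies wider knowledge of eligibility. The sentence on documenting exclusion reasons says individuals, a word Section 4.2 also uses for people approached before consent. Section 3.2 names the eligibility criteria before consent. The consent criterion itself presupposes that refusers' eligibility is known. The sickle cell service is consulted on every hospitalized patient with the disease, and age and ACS diagnosis are already checked before approach.

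Part of this stands. The wider denominator is obtainable, so a reader who infers that the pilot cannot test its exclusion limit, or that nothing is checked before consent, goes too far. But none of these sentences creates a step that records eligibility for people who decline or are missed. Section 3.2 lists conditions for randomization; Section 4.2 sets the order. The consent criterion needs the missing data but does not supply them.

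A reader might also infer that the exclusion rate will look better than it is, because the background section cites a 17% prevalence of pulmonary artery thrombosis in ACS and such patients might be passed over. The documents do not support this. Nothing says that they are passed over. The relevant exclusion covers only embolism found on CT done as standard of care, and a chest x-ray suffices to diagnose ACS. Withholding approach for that reason would in any case mean applying the criteria before consent.

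It is also fair that the rate is imprecise in a pilot of 20 under either order: 12/60 still spans 20% widely.

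**Conclusion.** The point holds as a mismatch between procedure and criteria. As written, formal screening covers about 25 of 60 admissions, about 58% have no eligibility data, and two prespecified feasibility criteria lack a recorded denominator. The exclusion rate in consenters may be higher or lower than the rate in ACS admissions; the documents do not settle which.

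The figures rest on 30 admissions a year, 20 randomized in two years and 20% excluded among consenters. The 12/60 comparison further assumes that every admission is notified and that the same rate applies throughout.

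A reader might infer that a go/no-go decision or a phase III accrual forecast would be wrong as a result. The documents state neither a go/no-go rule nor a forecast built on this rate; their stated inputs to later sample size planning are treatment effect and variance. What is at stake is the validity of two feasibility results. That is reason enough to correct the plan, and the correction leaves treatment, randomization and sample size untouched.

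**What to change.** - **Section 4.2:** with IRB permission for record review before consent, apply the Section 4.3 criteria from the chart to every ACS admission notified to the study. Keep a de-identified log of eligibility, each exclusion reason, whether the patient was approached, and the consent outcome. Keep the check after consent as confirmation before the envelope is opened.
- **Section 3.3:** define the 20% exclusion criterion as excluded / all notified ACS admissions, and the 80% consent criterion as consented / eligible, both counted on that log. Admissions never notified stay outside it and belong to the separate notification criterion.

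The cost is a protocol and IRB amendment and a short entry for about 30 admissions a year by existing staff, from records already in the chart. The reported exclusion and consent rates may turn out less favorable. The log should be in place from the first admission, because eligibility at the time may be hard to reconstruct later.

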The primary clinical outcome is duration of hospitalization. Secondary clinical outcomes include the duration of hypoxemia, duration of fever, duration of leukocytosis, duration of moderate to severe pain, total dose of opioids, and the number of red blood cell transfusions administered. Additional clinical outcomes will include the rate of transfer to the ICU, requirement for mechanical ventilation, and development of MODS.

Duration of hospitalization will be defined as beginning with randomization and measured in hours. Conclusion of hospitalization will be defined as the time of order entry into the inpatient electronic medical record system stating the patient is appropriate for medical discharge, per the discretion of the treating physician. Duration of hypoxemia will be defined as beginning with randomization and measured in hours. Hypoxemia will be defined as arterial oxygen saturation less than 90% according to pulse oximetry and/or the continued need for supplemental oxygen. If the patient's baseline arterial oxygen saturation is less than 90%, hypoxemia will be defined as a decrease in arterial oxygen saturation below the patient's baseline. Similarly, if

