4.6 Adverse Event Reporting

All adverse events (AE) experienced by study subjects are to be recorded on the CRF, regardless of the severity of the event or its relationship to study treatment. The AE reporting procedures are based on the CTCAE system, volume 4.03, 2010. Subjects will report any symptoms to the investigator, research staff, inpatient nursing staff, or treating physician. [name] will determine if symptoms qualify as an AE or SAE with confirmation by [name]. AEs will be classified as mild (does not interfere with routine activities), moderate (interferes somewhat with routine activities), or severe (impossible to perform routine activities). The following algorithm will be used to assess the causality of all AEs:

- **Not related:** The event can readily be explained by factors not involving UFH, and a temporal relationship with UFH does not exist.
- **Possibly related:** A clinical event, including laboratory test abnormality, with a reasonable time sequence to administration of UFH but which could also be explained by concurrent disease or other drugs or chemicals. Information on drug withdrawal may be lacking or unclear.
- **Probably related:** The temporal relationship between the administration of UFH is compelling, and the event cannot be explained by the subject's medical condition or other therapies.
- **Related:** The event follows a reasonable temporal sequence from the administration of UFH, follows a known or suspected response pattern to UFH, is confirmed by improvement upon stopping UFH, and reappears upon repeated exposure to UFH.

The investigator will follow up all AEs, regardless of severity, until satisfactory resolution. All subjects experiencing AEs will be monitored until symptoms subside and any abnormal laboratory values have returned to baseline, or until there is a satisfactory explanation for the changes observed, or until death, in which case a full pathologist's report will be supplied, if possible. Withdrawal from the clinical study and therapeutic measures shall be at the discretion of the investigator. As required by the IRB, if there is a serious, unexpected or adverse event that is determined to be associated with UFH, it will be reported to the IRB within 24 hours. If the event is not serious, unexpected or related to UFH, it will be reported within 5 days. All events must be assessed to determine the following:

- If the event meets the criteria for an SAE.

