- The relationship of the event to study treatment.
- The severity of the event.

An AE is any untoward medical occurrence in a subject in whom a pharmaceutical product is administered but does not necessarily have a causal relationship with the pharmaceutical product. An AE can therefore be any unfavorable and unintended sign (including an abnormal laboratory finding), symptom, or disease temporally associated with the use of a pharmaceutical product, whether or not related to the pharmaceutical product.²⁷ A SAE is any untoward medical occurrence that at any dose:

- Results in death.
- In the view of the investigator, places the subject at immediate risk of death.
- Requires inpatient hospitalization or prolongation of existing hospitalization.
- Results in persistent or significant disability/incapacity.
- Results in a congenital anomaly/birth defect.

An SAE may also be any other medically important event that, in the opinion of the investigator, may jeopardize the subject or may require intervention to prevent one of the other outcomes listed in the definition above.

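### Data collection ends at study withdrawal with no exception for discharge time, so the primary clinical outcome can be lost, possibly unevenly between arms

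*Combined protocol and SAP*

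**What the plan says.** Section 4.2 covers withdrawal in four sentences. The first gives participants the right to leave: "Study participants will be free to withdraw at any time by notifying a member of the research staff". The next sets the data rule: "Any data collected prior to the time of withdrawal will continue to be used, but no additional information will be collected". A third deals with blood samples, and the last adds "The reason and date of study withdrawal for all subjects will be recorded". No outcome is exempt from the data rule.

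Section 4.6, on adverse events, has a second route out of the study: "Withdrawal from the clinical study and therapeutic measures shall be at the discretion of the investigator". It gives no criteria. The same paragraph requires that "The investigator will follow up all AEs, regardless of severity, until satisfactory resolution", with no exception for subjects who have withdrawn.

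Section 3.3 defines the primary clinical outcome. Its start: "Duration of hospitalization will be defined as beginning with randomization and measured in hours". Its end: "Conclusion of hospitalization will be defined as the time of order entry into the inpatient electronic medical record system", when that order states that the patient is fit for medical discharge. Section 3.3 also says that the pilot is to supply treatment effect and variance for later sample size calculations. The only analysis set it defines is for safety, namely enrolled subjects who received any UFH. There is no efficacy set, no statement that subjects are analysed as randomized, and no rule for a missing or censored stay.

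**The concern.** Duration of hospitalization has no value until the discharge order is written. If collection stops before then, the outcome is missing even though the order will later sit in the hospital's own electronic record.

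Such losses need not be random. Treatment is open-label, and only Arm A has a study infusion that can cause complications or that a subject may want to end. Section 4.6 does ask for all adverse events in study subjects to be recorded, but its definition is built on exposure ("An AE is any untoward medical occurrence in a subject in whom a pharmaceutical product is administered") and its causality scale refers only to UFH. Withdrawal prompted by an adverse event could therefore fall more on Arm A. If the subjects lost also differ in length of stay, the mean and SD of the remaining subjects no longer describe the randomized arm.

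Comparisons are descriptive, so no test or error rate is affected. What is at stake is the pair of estimates that the pilot is meant to hand to the phase III design.

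**Working it through.** **Figures in the plan.** None bears directly on this point. The sample size of 20 (10 per arm, section 4.2) is stated to rest on clinical rather than statistical considerations. No SD, effect size, withdrawal rate or dropout allowance is given. The figures below are per-case illustrations in SD units.

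**Step 1. What the text implies for a withdrawn subject.**
- The outcome ends at the discharge order (3.3).
- Collection ends at withdrawal (4.2), and the reason and date are recorded.
- So withdrawal before the order leaves no observed value, and 3.3 does not say what is then done.

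**Step 2. What the text implies for a subject who only stops UFH.**
- Section 4.4 prescribes stopping UFH, not leaving the study, for major bleeding, anaphylaxis, a low platelet count and heparin-induced thrombocytopenia (HIT). For low platelets it allows UFH to be resumed within the study period.
- Section 3.1 counts hours off the infusion as an adherence measure.
- These passages presuppose a subject who is still in the study. No passage says so, or says that all outcomes continue to be collected.

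**Step 3. How often a heparin-related event may arise.** Using the rates in 4.4, the chance of at least one event among 10 UFH subjects is 1 − (1 − p)^10:
- bleeding, upper bound p = 0.03: 26%;
- HIT, p = 0.01 to 0.02: 10% to 18%;
- non-immune thrombocytopenia, p = 0.05 to 0.30: 40% to 97%. Section 4.4 stops UFH only at a lower platelet count than the one defining thrombocytopenia, so this overstates how often UFH would be stopped for it.

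These are chances of an event, not withdrawal rates.

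**Step 4. Effect of one loss on the Arm A mean.** Take ten stays with mean 0 and sample SD 1, and remove one at k. The remaining nine have mean −k/9.
- k = 1: −1/9 = −0.11 SD.
- k = 2: −2/9 = −0.22 SD.

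**Step 5. Effect of one loss on the Arm A SD.** The ten values have sum of squares 9. After removal it is 9 − k² − k²/9, divided by 8.
- k = 1: (9 − 1 − 0.111)/8 = 0.986, SD 0.993, a fall of under 1%.
- k = 2: (9 − 4 − 0.444)/8 = 0.569, SD 0.755, a fall of about 25%.

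**Step 6. Set against sampling error.** The standard error of the difference is √(1/10 + 1/10) = 0.447 SD with complete data and √(1/9 + 1/10) = 0.459 SD after one loss. The illustrated shift is a quarter to a half of the standard error.

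**Step 7. Possible consequence for phase III.** Assume a true effect of 0.5 SD, two-sided 5% and 80% power, with n per arm = 2(1.960 + 0.842)²/d².
- d = 0.5: 63 per arm.
- d inflated by 0.1 to 0.6: 44 per arm, true power 65%.
- d inflated by 0.2 to 0.7: 33 per arm, true power 53%.

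This holds only if the bias favours UFH, which is assumed.

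**The case against.** The strongest reply is that the protocol does separate stopping the drug from leaving the study. A reader might infer from 4.2 that anyone whose infusion is stopped loses all later data. Sections 3.1 and 4.4 do not support that: for the named heparin complications, the ones most specific to Arm A, they prescribe stopping UFH only. This stands, and it may keep the number affected small.

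A reader might also infer that safety follow-up ends at withdrawal. Section 4.6 requires all adverse events to be followed to resolution, so that reading fails too. What remains is a conflict: 4.2 allows no new information after withdrawal, while 4.6 demands it.

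Next, the data rule in 4.2 directly follows the sentence on withdrawal by the participant, where ending collection respects the subject's choice. Applying it to withdrawal by the investigator is the natural reading, since no other rule exists, but it is not spelled out. The consent pages are not in the file, so whether they address later access to records cannot be checked.

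The direction of bias is also open. It is tempting to say that long Arm A stays would drop out, flattering heparin and shrinking the SD. Nothing in the documents shows that those withdrawn would have long stays, and Arm B subjects may withdraw as well. Nor should the illustration be stretched to two losses at +2 SD and a shift of 4/8 = 0.50 SD. Two such values force the other eight to average −0.5, so the sum of squares is at least 8 + 2 = 10 and the sample SD at least √(10/9) = 1.05, which contradicts an SD of 1.

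Finally, lost data would count against the 90% completeness criterion in 3.3. That is only a partial safeguard. If completeness were judged by subjects with a discharge time, one loss leaves 19/20 = 95% and two leave 18/20 = 90%, and both meet the criterion. The protocol does not say how completeness is counted.

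**Conclusion.** The point holds as a gap in the rules. As written, a subject withdrawn before the discharge order has no primary clinical outcome. Investigator withdrawal has no criteria, no sentence keeps subjects off UFH in follow-up, and 4.2 and 4.6 conflict on adverse events after withdrawal. Losses could be unbalanced and related to length of stay, which would bias the effect and variance estimates meant for phase III.

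The size is conditional. One Arm A loss at +1 to +2 SD lowers that arm's mean by 0.11 to 0.22 SD, less than the 0.447 SD standard error of the difference. How many withdraw, from which arm and with what stays are assumptions that the documents do not supply. They do not support a claim that stopping UFH amounts to withdrawal, that safety follow-up is abandoned, or that the result will favour heparin.

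**What to change.** 1. In 4.2 and 4.6, state that stopping UFH for any reason is not study withdrawal, and that such subjects stay in follow-up for all outcomes and are analysed in their randomized arm. This leaves the clinical rules for stopping UFH as they are.
2. Ask subjects who withdraw for permission to keep reading discharge-order time, ICU transfer, mechanical ventilation and adverse events from the electronic record. End collection only for those who refuse.
3. Reconcile the data rule in 4.2 with the adverse event follow-up rule in 4.6, so that staff know which applies after withdrawal.
4. In 3.3, say how a discharge time that is still missing will be reported, and give the number by arm.

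The cost is a few sentences in the protocol, a consent-form change and some record abstraction. The sample size stays at 20 and no study procedure is added.
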